#### Crossover Subject Analyses

Data from subjects assigned to the low and medium dose groups, i.e. ‘crossover population,’ will be analyzed by within-subject t-tests comparing difference scores from primary endpoint in Stage 1 to secondary endpoint in Stage 2 (Table 3 and 4). The following measures total scores will be analyzed in this fashion: CAPS, PTGI, BDI-II, GAF, PSQI, DES-II, and NEO PI.

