# 6.2.10 Open-Label Study Segment for Low Dose and Medium Dosage Participants ("Stage 2")

Participants assigned to receive low dose or medium dose MDMA during Stage 1 will undergo three open-label MDMA-assisted psychotherapy sessions that follow a course and schedule similar to Stage 1 for the full dose group except that participants will

undergo one instead of three introductory sessions. After confirming consent and eligibility criteria, participants continuing to Stage 2 will meet with both investigators conducting psychotherapy for a single review and preparatory psychotherapy session before the first open-label MDMA-assisted psychotherapy session. If more than 8 weeks have passed since the primary endpoint, all measures will be repeated for a new baseline prior to the first open-label experimental session. Experimental sessions will be conducted according to procedures described in Section 6.2.3. During the first experimental session, subjects will receive a 100 mg initial dose of MDMA and may receive a 50mg optional supplemental dose of MDMA. At the beginning of each of the second and third experimental sessions, the co-therapists, in consultation with the subject, will decide whether to administer an initial dose of 100 mg or 125 mg initial dose of MDMA. If a 100mg initial dose of MDMA is selected, an optional supplemental dose of 50mg MDMA may be administered. If a 125mg initial dose of MDMA is selected, an optional supplemental dose of 62.5mg MDMA may be administered. If the PI decides not to administer the optional supplemental dose and/or the optional clinical titration dose in a given experimental session, the unused capsules will be kept in their respective inner envelopes inside of the primary container in the safe.

Integrative sessions will be conducted according to procedures described in Sections 6.2.4 and 6.2.6. Phone calls will be conducted according to procedures described in Section 6.2.5.At the secondary endpoint based on procedures described in Section 6.2.7, the Independent Rater will administer the CAPS and GAF. Subjects will complete the BDI-II, PSQI, PTGI (in reference to the start of the study), and DES-II.Administration of the CAPS may be recorded to video.

Investigators will follow the most recent treatment manual in all matters relating to the Open-Label Stage 2 experimental psychotherapy sessions

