# 6.2.11 Assessment Two Months after Third Open-Label Session (End of Stage 2)

All participants in Stage 2 will be assessed by the independent rater two months after their final open-label session. At that visit, the independent rater will administer the CAPS, which may be recorded to video, and assess participants on the GAF, and participants will complete the BDI-II, PTGI (in reference to the start of the study), PSQI, DES-II, and NEO-PI. Participants will also complete C-SSRS and RRPQ with the therapists. Participants will provide their perception of the experimental sessions. Adverse Events and medications will be collected as described in Sections 8 and 9 of the protocol. The visual analog scale will be used to collect changes in pre-existing tinnitus and chronic pain symptoms.

Subjects will receive a memory aid card for use between this visit and the 12-month follow up. Subjects will use this card to record AEs, medications, and changes in psychiatric status that they will be asked about at the termination visit. Memory aids will not be collected. Subjects may return to taking psychiatric medications from this point onward if necessary.

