When each subject completes the evaluation at the primary endpoint, the blind will be broken for that subject. Subjects who had been assigned to receive low dose or medium dose MDMA will subsequently have the opportunity to enroll in the open-label study arm, or “Stage 2.” Stage 2 must start within a maximum of 5 months after the subject finishes Stage 1. The open-label study arm will follow a similar sequence of events and procedures, except that there will be a single preparatory session, and all three MDMA-assisted psychotherapy sessions will be open-label. Subjects will receive an initial dose of 100 mg MDMA in the first experimental session, and one of two active doses of MDMA that are clinically titrated by the CI during the second and third open-label experimental sessions that will otherwise follow the same sequence of events (See Time and Events Table). Outcome measures except for the NEO PI will be repeated one month after the second Stage 2 experimental session, and all outcome measures will be repeated at the end of Stage 2.

The study will conclude with a one-year follow-up occurring 12 months after the final experimental session of Stage 1 for subjects who received full dose MDMA or who elected not to enroll in Stage 2 after receiving either the medium or low doses in Stage 1. Subjects who enrolled in Stage 2 will have their final follow-up 12 months after the final open-label experimental session. Outcome measures will be repeated at the 12-month follow-up, as well as a questionnaire concerning self-reported long-term effects of study participation.

Sub-studies in a select group of subjects in this study may be conducted for exploratory purposes. Subjects will complete a separate consent process if they chose to participate in these studies.

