| Complete Randomization Procedure           |   |            |                          | X B         |                        |                        |                         |                  |                                |                            |  |
| CAPS, GAF, BDI-II, PTGI, PSQI, DES-II (IR) | X   |            |                          |                        |                        |                        |                         | X                |                                |                            | X  |
| NEO PI (Ind. Rater)                        | X   |            |                          |                        |                        |                        |                         | X                |                                |                            |  |
| C-SSRS                                     |   | X          | X                        | X C, D, E   | X I         | X C, D, E   | X I          | X                | X C, D, E           | X I             | X  |
| Administer IP Drug + Therapy, SOCQ         |   |            |                          | X                      |                        | X                      |                         |                  | X                              |                            |  |
| Monitoring of BP, Heart rate and Temp.     |   |            |                          | X                      |                        | X                      |                         |                  | X                              |                            |  |
| SUD  |   |            |                          | X F, E      |                        | X F, E      |                         |                  | X F, E              |                            |  |
| Beliefs of Condition Assignment            |   |            |                          |                        | X K         |                        | X K          |                  |                                | X K             |  |

|   |                |   |                  |                  |                  |                  |                  |                |                  |                  |                |

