| General Well-Being                         | X                                  | X                      | X                       | X                      | X                       |                              | X                      | X                       | X   |   |
| Drug Screen                                |                                    | X                      |                         | X                      |                         |                              | X                      |                         |   |   |
| Pregnancy Screen (if applicable)           |                                    | X                      |                         | X                      |                         |                              | X                      |                         |   |   |
| CAPS, GAF, BDI-II, PTGI, PSQI, DES-II (IR) | Use V13*                           |                        |                         |                        |                         | X                            |                        |                         | X   | X   |
| NEO PI with Ind. Rater                     | Use V13*                           |                        |                         |                        |                         |                              |                        |                         | X   | X   |
| C-SSRS                                     | X                                  | X C, D, E   | X G          | X C, D, E   | X G          |                              | X C, D, E   | X G          | X   | X   |
| Administer IP Drug + Therapy, SOCQ         |                                    | X                      |                         | X                      |                         |                              | X                      |                         |   |   |
| Monitoring of BP, Heart rate and Temp.     |                                    | X                      |                         | X                      |                         |                              | X                      |                         |   |   |
| SUD  |                                    | X D, F      |                         | X D, F      |                         |                              | X D, F      |                         |   |   |

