### **8.9.2.2 Secondary Efficacy Analyses at Secondary Endpoints**

#### Assess 3 vs. 2 experimental MDMA sessions

For the CAPS, PTGI, BDI-II, GAF, PSQI, DES-II, and NEO PI, the absolute changes in the measures from the primary endpoint to end of Stage 1 for the 125 mg group will be compared with t-tests. In the crossover subjects (30 mg and 75 mg group) the absolute

changes in the measures from the secondary endpoint to end of Stage 2 will be compared with t-tests.

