#### Long-term Follow-up

For the CAPS, PTGI, BDI-II, GAF, PSQI, DES-II, and NEO PI, the absolute changes in the measures from baseline to the long-term follow-up visit (one year post final experimental year) will be compared with t-tests. The absolute changes in the measures from long-term follow-up to End of Stage 1 (visit 18, 125 mg) or long-term follow-up compared to End of Stage 2 (visit 33, 30 and 75 mg) will be compared with within-subject t-tests.

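### SAP 8.9.2.2 tests NEO PI change to and from the Stage 2 secondary endpoint (V28), where it is not collected, so the Stage 2 versus Stage 1 personality comparison in crossover subjects has no runnable named test

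*SAP*

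**What the plan says.** **Objective.** Protocol 3.2 and SAP 3.2 both set out to compare NEO PI personality scores throughout Stage 2 with Stage 1 in crossover subjects. The SAP places this among its exploratory objectives; the protocol lists it outside its exploratory block.

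**Analysis.** SAP 8.9.2.2 applies one list of seven measures to all its contrasts.

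- *Crossover Subject Analyses:* within-subject t-tests from the Stage 1 primary endpoint to the Stage 2 secondary endpoint. "The following measures total scores will be analyzed in this fashion: CAPS, PTGI, BDI-II, GAF, PSQI, DES-II, and NEO PI".
- *Assess 3 vs. 2 experimental MDMA sessions:* for the 125 mg group, change from V13 to the end of Stage 1 (V18). For crossover subjects, "changes in the measures from the secondary endpoint to end of Stage 2 will be compared with t-tests". NEO PI is on the list.
- *Long-term Follow-up:* baseline to 12 months in all subjects, then 12 months against the end of the subject's last stage, beginning "The absolute changes in the measures from long-term follow-up to End of Stage 1 (visit 18, 125 mg" and continuing with V33 for the 30 and 75 mg groups. NEO PI is on this list too.

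**Collection.** SAP 4.0 states: "Outcome measures except for the NEO PI will be repeated one month after the second Stage 2 experimental session". Protocol 5.0 has the same sentence. Protocol 6.2.10 names the self-report measures at the secondary endpoint without NEO PI: "Subjects will complete the BDI-II, PSQI, PTGI (in reference to the start of the study), and DES-II". At the end of Stage 2, Protocol 6.2.11 includes it: "participants will complete the BDI-II, PTGI (in reference to the start of the study), PSQI, DES-II, and NEO-PI". In the SAP's Stage 2 Time & Events table, the row "NEO PI with Ind. Rater" carries V13 forward as the starting value, has entries at the end of Stage 2 and at one year, and has none at V28.

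**Score.** SAP 7.1 and 8.9.2.1 define NEO PI by its five factors. Neither defines a total.

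**The concern.** The crossover contrast is the only test in the SAP that sets Stage 2 personality scores against Stage 1, and one of its two time points has no NEO PI assessment. The V28-to-V33 contrast has the same gap. Reusing a single list of measures appears to have hidden the fact that NEO PI is given less often than the other six.

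At stake is prespecification. When the V28 test comes back empty, the analyst must either drop it or choose another contrast. Under SAP 8.0 an analysis not identified in the SAP has to be reported as post hoc. SAP 8.10 allows no further analyses of the data set after the initial ones, apart from exploratory post-hoc work. A comparison that both documents set as an objective would then lose its prespecified status, although suitable data are already scheduled.

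**Working it through.** The plan gives no figure to reproduce. The check sets each NEO PI contrast in SAP 8.9.2.2 against the visits at which NEO PI is scheduled.

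**Inputs**

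- Group sizes (SAP 5.0): 12 at 125 mg, 6 at 75 mg, 6 at 30 mg, so at most 6 + 6 = 12 crossover subjects.
- NEO PI visits, crossover subjects (Time & Events tables; Protocol 6.0, 6.2.7, 6.2.11, 6.2.12): baseline, V13, V33, 12 months = 4. The other six measures add V28 = 5.
- NEO PI visits, 125 mg, if the Stage 1 table governs: baseline, V13, 12 months = 3. The other six add V18 = 4.
- Any repeat assessment before Stage 2 is not counted.

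**Rule.** Maximum pairs = group size if the measure is scheduled at both visits, otherwise 0.

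| Contrast | Group | Visits needed | Max NEO PI pairs | Max pairs, other six measures |
|---|---|---|---|---|
| Crossover | 30/75 mg | V13, V28 | 0 | 12 |
| Third session | 30/75 mg | V28, V33 | 0 | 12 |
| Third session | 125 mg | V13, V18 | 0 if the table governs | 12 |
| Long-term, from end of Stage 1 | 125 mg | V18, 12 months | 0 if the table governs | 12 |
| Long-term, from end of Stage 2 | 30/75 mg | V33, 12 months | 12 | 12 |
| Long-term, from baseline | all | baseline, 12 months | 12 + 12 = 24 | 24 |
| *Not named in the SAP* | 30/75 mg | V13, V33 | 12 | 12 |

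**Count.** There are 6 named contrasts. Two need V28 and certainly have no NEO PI data. Two more need V18 and have none if the Stage 1 table governs. Crossover subjects enter 4 of the 6, of which 4 − 2 = 2 can be run: baseline to 12 months, and V33 against 12 months. Both serve the long-term objective, and neither compares Stage 2 with Stage 1.

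**Is the V28 gap an extraction artefact?** No. The exclusion is an explicit sentence in both documents and agrees with the visit description, so the conclusion does not rest on a blank table cell.

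**V18 in the 125 mg group.** Here the documents conflict. A general sentence in SAP 4.0 and Protocol 5.0 places outcome assessments two months after the third open-label session, directly after a sentence that names NEO PI. Against it, the Stage 1 table has no V18 entry for NEO PI, Protocol 6.2.8 does not list it at V18, and the personality schedule in Protocol 6.0 omits that visit.

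**The case against.** The strongest reply is that little is lost. The objective is to assess personality in Stage 2 compared with Stage 1; it does not demand a t-test at V28. SAP 8.9 already promises descriptive statistics by treatment group for every endpoint, and Protocol 12.0 plans effect sizes for all outcome measures at the end of Stage 2. SAP 1.0 defines exploratory analyses as either inferential or descriptive, and this is a pilot of 24 meant to yield effect sizes. An empty test would be noticed at once and could mislead nobody.

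Most of that stands, and it rules out the tempting conclusion that the objective cannot be met at all. It does not rescue the two named tests, which have no data, or supply a prespecified substitute.

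Three other inferences should also be resisted.

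- *That the V18 gap adds to the crossover problem.* It does not. Footnote J of the Stage 1 table says low and medium dose subjects do not have visits 14 to 18. V18 bears only on 125 mg contrasts, and whether NEO PI is missing there is unresolved.
- *That the start value of the crossover test is undefined, because measures are repeated when Stage 2 starts more than 8 weeks after V13.* The SAP names the Stage 1 primary endpoint as the start, and SAP 8.9.1 and 8.9.2.1 identify the primary outcome timepoint as visit 13.
- *That bias or a false finding follows.* Missing data at V28 yield no result, not a wrong one.

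**Conclusion.** The point holds for V28. Two of the six NEO PI contrasts in SAP 8.9.2.2 have zero possible pairs, and one of these is the only named Stage 2 versus Stage 1 personality test. The reference to total scores is a smaller defect in the same sentence, since the SAP defines only five factors for NEO PI. Two further contrasts, in the 125 mg group only, depend on an unreconciled statement about V18 and should not be counted as certain.

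The effect is confined to secondary and exploratory analyses of one instrument, in at most 12 crossover subjects. The primary CAPS comparison at V13 is untouched. The correction is worth making because a stated objective regains a prespecified test at almost no cost. The maximum of 12 pairs assumes that all low and medium dose subjects complete Stage 2 and have both assessments.

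**What to change.** In SAP 8.9.2.2:

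1. *Crossover Subject Analyses:* take NEO PI out of the V13-to-V28 list and test its five factor scores from V13 to V33 by within-subject t-test. State that this contrast spans all three Stage 2 sessions and compares one month after session 2 with two months after session 3, so it is not matched in timing as V13 to V28 is for the other measures.
2. *Assess 3 vs. 2 experimental MDMA sessions:* remove NEO PI. The third-session objective in SAP 3.2 does not name it.
3. *Score:* refer to the five factor scores for NEO PI wherever the section now asks for total scores.

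Separately, for the 125 mg group, reconcile the general sentence in SAP 4.0 and Protocol 5.0 with the Stage 1 table, Protocol 6.0 and Protocol 6.2.8 on whether NEO PI is collected at V18. If it is not, remove NEO PI from the V18 versus 12-month test and keep the baseline-to-12-month test.

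The cost is a short SAP revision, made before the data are analysed, and at most a one-line schedule alignment between the documents. No visit or assessment is added: NEO PI is already scheduled at V13, V33 and 12 months.

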#### Long-term Follow-up

For the CAPS, PTGI, BDI-II, GAF, PSQI, DES-II, and NEO PI, the absolute changes in the measures from baseline to the long-term follow-up visit (one year post final experimental year) will be compared with t-tests. The absolute changes in the measures from long-term follow-up to End of Stage 1 (visit 18, 125 mg) or long-term follow-up compared to End of Stage 2 (visit 33, 30 and 75 mg) will be compared with within-subject t-tests.

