### 12.0 Data Analysis

The Sponsor will judge the clinical and statistical significance of the study and estimate effect size and statistical power based on a comparison of observer-blind data collected at baseline and the primary endpoint using the primary outcome measure, which is the CAPS.

The sample selection is expected to produce acceptably homogeneous groups due to their diagnosis of with PTSD with CAPS scores of at least 50 who have not responded to treatment. There is no expectation that conditions will differ significantly in composition by gender, race or ethnicity, duration of PTSD diagnosis or presence versus absence of other permitted psychiatric disorders, as depression.

The sponsor will examine individual CAPS, BDI-II, PTGI, PSQI, DES-II and GAF scores at baseline and the primary endpoint, in low dose, medium dose and full dose conditions. Descriptive statistics will be calculated for all measurements overall and by condition. Distributional characteristics will be examined for outliers and extreme values and, if either is evident. If outliers are found in primary or secondary outcome measures, the sponsor will perform analyses with and without the outlying data. Effect sizes for all outcome measures for primary endpoint, Stage 1, secondary endpoint, end of Stage 2, and 12-month follow-up will be estimated using Cohen's techniques.

All analyses of data from the primary endpoint will contain blinded data. Analysis of variance will be used to compare Global CAPS scores by dose condition at the primary endpoint.

Analysis of variance, or nonparametric analysis if assumptions are not met, will be used to compare the dose conditions for change in BDI-II, PTGI, PSQI, GAF, DES-II and NEO PI scores separately. If scores cannot be examined sufficiently in this model, then analyses will compare available data through the use of difference scores.

The sponsor will examine open-label data collected two months after the third Stage 1 experimental session. The sponsor will perform a within-subject analysis of full dose participants.

Subjects who discontinue treatment prior to the primary endpoint will be asked to complete an outcome assessment prior to continuing to the long-term follow-up. The data from these subjects will be tested for equivalence to data from subjects completing the study per protocol. If found to be equivalent, data from these subjects will be presented as

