- Assess long-term effects of receiving active dose MDMA on PTSD symptoms via CAPS, posttraumatic growth via PTGI, personality changes via NEO PI, depression

symptoms via BDI-II, global functioning via GAF, and sleep quality via PSQI one year after the final experimental session for each subject.

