| Perception of Third Session                        |   |                  |                  |                  |                  | X              |                  |                  | X              |                |
| Complete Stage 2, go to 1yr F/U                    |   |                  |                  |                  |                  |                |                  |                  | X              |                |
| RRPQ   |   |                  |                  |                  |                  |                |                  |                  | X              |                |
| Issue Memory Aid Card                              |   |                  |                  |                  |                  |                |                  |                  | X              |                |
| Follow-up Questionnaire                            |   |                  |                  |                  |                  |                |                  |                  |                | X              |
| Termination Visit                                  |   |                  |                  |                  |                  |                |                  |                  |                | X              |

\* If Visit 19 is more than 8 weeks after V13 then the measures from V13 will need to be repeated prior to starting Stage 2 A =First session is 1 day after Exp session B =Approximately 6 hours post MDMA C =At the beginning of the session D =As needed E =Approximately every 60 minutes F = Given on 2nd integrative session only G = For 7 days post Exp. Session, C-SSRS D2 and D7 of calls only, General well being for all 7 days H=CAPS may be videotaped I= Only in subjects with pre-existing tinnitus and/or chronic pain.

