### 8.5 Baseline Values

Baseline values are from screening/baseline visit for all measures, except C-SSRS. For C-SSRS, pre-enrollment scores will be used as a measure of ‘lifetime’ suicidal ideation and behavior, and preparatory session 2 (visit 3) pre-drug Since Last Visit C-SSRS scores will be used as ‘baseline.’ If a subject was not administered the C-SSRS at preparatory session 2 (visit 3), then ‘baseline’ scores will be from preparatory session 3 (visit 4).

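### The screening-to-12-month test in SAP 8.9.2.2 includes the Stage 1 response of crossover subjects, so it does not match the active-dose objective, and no planned test runs from the Stage 2 start to 12 months

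*SAP*

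**What the plan says.** SAP 3.2 gives the objective: "Assess long-term effects of receiving active dose MDMA on PTSD symptoms via CAPS", with further measures, one year after each subject's final experimental session. The SAP lists it among the exploratory objectives. The test itself sits under Secondary Efficacy Analyses, in the Long-term Follow-up paragraph of 8.9.2.2: "the absolute changes in the measures from baseline to the long-term follow-up visit (one year post final experimental year) will be compared with t-tests". That paragraph names no population, no grouping, and no separate reference for subjects who crossed over.

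SAP 8.5 supplies the meaning of baseline: "Baseline values are from screening/baseline visit for all measures, except C-SSRS".

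Subjects assigned 30 or 75 mg may enter open-label Stage 2. They receive 100 mg at the first session and then, per SAP 4.0, "one of two active doses of MDMA that are clinically titrated by the CI". Stage 2 may begin up to 5 months after Stage 1 ends. Both schedules use the V13 (primary endpoint) scores as the Stage 2 starting values by default. If more than 8 weeks have passed, protocol 6.2.10 says that "all measures will be repeated for a new baseline prior to the first open-label experimental session". The footnote to the SAP's Stage 2 Time & Events table agrees: "the measures from V13 will need to be repeated prior to starting Stage 2". The Crossover Subject Analyses paragraph in SAP 8.9.2.2 does not mention the repeat. It specifies t-tests "comparing difference scores from primary endpoint in Stage 1 to secondary endpoint in Stage 2".

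**The concern.** For a subject randomised to 125 mg, screening is the last efficacy assessment before the first active dose, so change from screening is a natural match to the objective. For a subject randomised to 30 mg, screening comes before three preparatory sessions, two blinded sessions and six integrative sessions, all completed before the first 100 mg dose. Any improvement over that period counts towards the 12-month change. Some improvement is plausible. The psychotherapy is intensive, and entry requires a CAPS score of at least 50, so regression to the mean would also fall between screening and V13.

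A significant 12-month change in these arms could therefore appear even if Stage 2 added nothing. A subject who declines Stage 2 also has a 12-month visit. If assigned 30 mg, that subject's change contains no active dose at all.

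The estimate may also be carried forward. Protocol 12.0 says effect sizes for "end of Stage 2, and 12-month follow-up will be estimated using Cohen's techniques", without naming the reference timepoint, and SAP 6.0 intends the study's effect sizes to inform the power of later trials.

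**Working it through.** **Allocation.** SAP 5.0 gives 24 evaluable subjects at 2:1:1. 24 × 2/4 = 12 at 125 mg, and 24 × 1/4 = 6 at each of 75 and 30 mg. This reproduces the stated 12/6/6. Up to 6 + 6 = 12 of 24 can cross over. The documents give no power figure to reproduce.

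**Planned tests for crossover subjects, by interval (SAP 8.9.2.2).**
- Crossover Subject Analyses: V13 to V28 (secondary endpoint).
- Three versus two sessions: V28 to V33 (end of Stage 2).
- Long-term Follow-up, first test: screening to 12 months.
- Long-term Follow-up, second test: V33 to 12 months, which addresses durability only.

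None runs from the Stage 2 start to 12 months. For NEO PI the gap is wider. It is not collected at V28 (SAP 4.0), so neither the V13-to-V28 nor the V28-to-V33 test can be computed for it. In crossover subjects, screening to 12 months is then the only NEO PI test that spans active dosing.

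**Decomposition.** Let D be the mean improvement from screening to the Stage 2 start, and A the mean improvement from there to 12 months. The screening-based test estimates D + A. The Stage 2 portion is A.

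**Size.** Protocol 12.1 says no estimate exists for change in CAPS at the low or medium dose, so D, A and the SD of change are all assumptions. Take A = 0 and a two-sided within-subject t-test at 0.05. The test statistic is noncentral t with n − 1 degrees of freedom and noncentrality (D/SD) × √n. For n = 12, SD = 25 and D = 20, the noncentrality is 0.8 × 3.464 = 2.77 and the rejection rate is 0.714.

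| n | SD | D = 0 | D = 10 | D = 20 |
|---|---|---|---|---|
| 12 | 20 | 0.050 | 0.353 | 0.883 |
| 12 | 25 | 0.050 | 0.245 | 0.714 |
| 12 | 30 | 0.050 | 0.184 | 0.558 |
| 6 | 20 | 0.050 | 0.171 | 0.507 |
| 6 | 25 | 0.050 | 0.127 | 0.356 |
| 6 | 30 | 0.050 | 0.103 | 0.265 |

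The rows with n = 12 assume that everyone in both lower-dose arms crosses over. The rows with n = 6 apply to one arm alone. Measured from the Stage 2 baseline the rate is 0.05 throughout, which follows directly from setting A = 0.

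**Effect size.** With A = 20 and SD = 25 (both assumed), the Stage 2 portion is 20/25 = 0.8. From screening it becomes (10 + 20)/25 = 1.2 for D = 10 and (20 + 20)/25 = 1.6 for D = 20.

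**Pooling.** If all 24 were pooled, which the SAP does not state, the mean would shift by 12/24 × D, that is 5 or 10 points for D = 10 or 20. If only the 30 mg arm is affected, the shift is 6/24 × D, that is 2.5 or 5 points.

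**The case against.** Change from screening to 12 months is a legitimate summary of the whole study course, and the Long-term Follow-up paragraph does not itself call it an active-dose effect. For measures other than NEO PI, the intervals V13 to V28, V28 to V33 and V33 to 12 months are each tested and together span the missing period. SAP 8.9 also requires descriptive statistics by treatment group, so the Stage 1 change will be visible by arm. All of this stands and limits the seriousness. It does not supply the one contrast that the objective calls for.

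A reader might make three stronger inferences that the documents do not support.

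- *That the Stage 2 baseline is never used.* V13 is the default Stage 2 baseline and the crossover test starts from it. The repeat is required only after more than 8 weeks. What is missing is any instruction in SAP section 8 to use the repeat when it exists, and any 12-month test from either reference.
- *That half the sample is certainly misclassified.* No passage says that 75 mg is not an active dose. SAP 3.2 has active-dose subjects giving perceptions at the primary endpoint, and the schedule restricts that item to full-dose subjects. This suggests that 75 mg is not counted, but does not settle it. The mismatch is clear for the 30 mg arm.
- *That a Stage 2 baseline would isolate the drug effect.* It would not. Change after that point also contains Stage 2 psychotherapy, the passage of a year, and any psychiatric medication resumed after Stage 2 (allowed by protocol 6.2.11). There is no concurrent control. The 125 mg arm, measured from screening, keeps its own regression to the mean and preparatory therapy.

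**Conclusion.** The point holds as a mismatch between an objective and its test. Even if the SAP is followed exactly, the only baseline-to-12-month test mixes the Stage 1 response with the later response to 100 or 125 mg. This affects the 6 subjects at 30 mg, and up to 12 of 24 if 75 mg is not active. The crossover test also starts from a V13 score that the protocol treats as out of date once more than 8 weeks have passed.

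The size is not known. For an assumed Stage 1 change of 10 to 20 CAPS points, SD 20 to 30 and no later effect, the screening-based test in 12 subjects rejects in about 18% to 88% of trials. In one arm of 6 the range is about 10% to 51%. If the Stage 1 change is zero, there is no error. These figures illustrate the consequence and do not predict this trial.

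The primary analysis at V13 is unaffected, the objective is listed as exploratory, and the study is a pilot. The point is minor to moderate.

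**What to change.** 1. In SAP 8.5, define a Stage 2 baseline for the efficacy measures: the repeated pre-Stage 2 measures when taken, otherwise V13.
2. Use that baseline in Crossover Subject Analyses.
3. In Long-term Follow-up, add a within-subject test from the Stage 2 baseline to 12 months for crossover subjects, reported by Stage 1 arm, as their analysis for the active-dose objective. Reporting by arm keeps the result readable whether or not 75 mg is regarded as active.
4. Keep screening-to-12-month change as a whole-course summary by arm, and show Stage 2 decliners separately.
5. State that the added contrast removes the Stage 1 change but is uncontrolled, and so does not by itself isolate a drug effect.

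The cost is a revision of the relevant SAP paragraphs and one added analysis. No new visits or data are needed, because V13 and any repeat measures are already in the schedule. The sponsor should expect a smaller 12-month effect in crossover subjects if they improved during Stage 1.
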